13.2.1 Toxicity monitoring for phase II study

Sequential boundaries will be used to monitor dose-limiting toxicity rate, based on the method described in Ivanova, Qaqish and Schell (Continuous Toxicity Monitoring in Phase II Trials in Oncology, Biometrics 61, 540-545, 2015[46]). This is a Pocock-type boundary where the same significance level is used for all looks. For practical implementation, we will look at the toxicity data in real time for every 3 patients, separately among the two phase II cohorts.

A DLT rate of 20% would be considered as acceptable while a DLT rate of 35% would be considered as too high and unacceptable. The type I error is chosen to be 10% and the power is chosen to be 80%. The accrual will be halted if excessive numbers of dose-limiting toxicities are seen, that is, if the number of dose-limiting toxicities is $>$ the following boundary b out of n patients currently studied:

- for the Flt3mut cohort, the boundary will be $b/n=2/3$, 3/6, 4/9, 5/12, 6/15, 7/18, 7/20;
- for the Flt3WT cohort, the boundary will be $b/n=2/3$, 3/6, 4/9, 5/12, 5/15, 6/16.

For example, if among the first 6 patients, there are more than 3 DLTs, then the accrual for the corresponding cohort would be paused. This will be looked at separately for the Flt3 WT and mutant cohorts.

Based on this rule, for the Flt3mut cohort, if the “true” DLT rate is 20%, then the probability of early stopping is about 4.8% with expected sample size of 19.5. If the “true” DLT rate is 35%, then the probability of early stopping is about 37% with expected sample size of 16.3. For the Flt3WT cohort, if the “true” DLT rate is 20%, then the probability of early stopping is about 7.3% with expected sample size of 15.6. If the “true” DLT rate is 35%, then the probability of early stopping is about 45.7% with expected sample size of 13.6.

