14. TRIAL MANAGEMENT

14.1 Data and Safety Monitoring Plan (DSMP)

The study will be conducted in accordance with the Indiana University Melvin and Bren Simon Cancer Center's (IUSCC) DSMP for High Risk Phase I/II Trials.

BTCRC AHQ facilitated oversight activities for Phase I/II High Risk Trials includes:

- Review and processing of all AEs requiring expedited reporting as defined in the protocol
- Provide trial accrual progress, safety information, and data summary reports to the sponsor-investigator. For any increase in frequency of grade 3 or above adverse events (above the rate reported in the Investigator Brochure or package insert), the sponsor investigator will notify BTCRC AHQ who will notify the DSMC Chair immediately. The notification will include the incidence of study adverse events, grades, and attributions, as well as investigator statements regarding comparison with risks per the IB/ package insert.
- Notify participating sites of adverse events potentially requiring expedited reporting and subsequent DSMC recommendations for study modifications.
- Investigators will conduct continuous review of data and patient safety.
- BTCRC AHQ will coordinate weekly (Phase I) meetings (Safety Calls) or monthly (Phase II) meetings which will include representation from each accruing site.
 - These meetings should include review of data, the number of subjects and significant toxicities as described in the protocol. BTCRC AHQ should maintain meeting minutes and attendance for submission to the DSMC upon request.
- Conduct the trial across all participating sites in accordance with the requirements set forth in the IUSCC DSMP.

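### The Phase II toxicity rule is stated to have 80% power at a 35% DLT rate, but its listed boundaries are crossed only about 46% of the time

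*Combined protocol and SAP*

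**What the plan says.** Section 13.2.1 (Toxicity monitoring for phase II study) sets up a Pocock-type sequential boundary on the DLT rate, with a look after every 3 patients, separately in each cohort. It fixes the two rates to be distinguished: "A DLT rate of 20% would be considered as acceptable while a DLT rate of 35% would be considered as too high and unacceptable". It then states the error rates: "The type I error is chosen to be 10% and the power is chosen to be 80"%.

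Accrual is halted when the number of DLTs is greater than b among n patients. After a first boundary of 2/3 in both cohorts, the list continues "3/6, 4/9, 5/12, 6/15, 7/18, 7/20" for FLT3-mutant and "3/6, 4/9, 5/12, 5/15, 6/16" for FLT3-WT. A worked example confirms the strict inequality: "For example, if among the first 6 patients, there are more than 3 DLTs", accrual pauses.

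The section closes with what the rule delivers. At a true rate of 35% in the mutant cohort, "then the probability of early stopping is about 37% with expected sample size of 16.3"; in the WT cohort, "then the probability of early stopping is about 45.7% with expected sample size of 13.6". At 20% it gives 4.8% (expected sample size 19.5) and 7.3% (15.6).

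**The concern.** For a rule that stops for toxicity, power is the probability of crossing a boundary when the DLT rate is the unacceptable one. The same short section therefore gives two answers to one question: 80% in the design sentence, and 37% and 45.7% in the results. Nothing reconciles them, and the text does not say that 80% was a target that was missed.

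This is the only numeric toxicity boundary for Phase II. A DSMC or IRB member who relies on the 80% would believe that an unacceptable DLT rate escapes the rule one time in five. By the rule's own boundaries it escapes more than half the time.

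**Working it through.** **Inputs.** From section 13.2.1: acceptable rate p0 = 0.20, unacceptable rate p1 = 0.35, halt if DLTs > b, and the boundaries b/n:

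- mutant: 2/3, 3/6, 4/9, 5/12, 6/15, 7/18, 7/20
- WT: 2/3, 3/6, 4/9, 5/12, 5/15, 6/16

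The cohort maxima of 20 and 16 are those in section 13.2 and the synopsis.

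**Method.** Exact binomial recursion. Start with 0 DLTs. Between looks, add a Binomial(m, p) count for the m new patients. At each look, remove the probability of all paths with DLTs > b; call this s(n). Then:

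- P(cross) = Σ s(n)
- E[N] = Σ n·s(n) + N_max·(1 − Σ s(n))

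**Crossing probability by look at p = 0.35**

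| n | Mutant | WT |
|---|---|---|
| 3 | 0.0429 | 0.0429 |
| 6 | 0.0863 | 0.0863 |
| 9 | 0.0771 | 0.0771 |
| 12 | 0.0645 | 0.0645 |
| 15 | 0.0539 | 0.1859 |
| 18 (mutant) / 16 (WT) | 0.0456 | 0 |
| 20 (mutant) | 0.0858 | – |
| **Total** | **0.4560** | **0.4567** |

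The first entry can be checked by hand: more than 2 of 3 means 3 of 3, and 0.35³ = 0.0429. The WT look at 16 adds nothing, because a cohort that continues past 15 patients has at most 5 DLTs, so at most 6 of 16, which is not more than 6.

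**The plan's own figures come first, and they reproduce.** The printed mutant probabilities count only stops before the last look.

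| Cohort, DLT rate | Stopping, printed | Stopping, recomputed | E[N], printed | E[N], recomputed |
|---|---|---|---|---|
| Mutant, 20% | 4.8% | 4.75% | 19.5 | 19.48 |
| Mutant, 35% | 37% | 37.0% | 16.3 | 16.34 |
| WT, 20% | 7.3% | 7.35% | 15.6 | 15.63 |
| WT, 35% | 45.7% | 45.7% | 13.6 | 13.60 |

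Counting the mutant look at 20 as well gives 5.83% at a 20% rate and 45.6% at a 35% rate.

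**The 80% does not reproduce.**

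- Shortfall, all looks counted: 80 − 45.6 = 34.4 points (mutant) and 80 − 45.7 = 34.3 points (WT).
- Reading the rule as DLTs ≥ b gives 70.0% and 70.6%, still below 80%. Type I error rises to 21.8% and 24.4%, and E[N] at 35% becomes 11.61 and 10.00, which does not match the printed values. The section did not use that reading.

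**Nor can it be reached at these sizes.** Any sequential rule on at most n patients is a test on those n outcomes, so it cannot beat the most powerful 10%-level test on the total DLT count, including one that randomises at the cut-off.

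- n = 20: rejecting at ≥ 7 DLTs has alpha 0.0867 and power 0.5834. The unused alpha is spent at exactly 6 DLTs (probability 0.1091 at p0 and 0.1712 at p1): (0.10 − 0.0867)/0.1091 = 0.122, which adds 0.122 × 0.1712 = 0.021. Ceiling 0.604.
- n = 16: rejecting at ≥ 6 has alpha 0.0817 and power 0.5100. At exactly 5 (0.1201 and 0.2008): (0.10 − 0.0817)/0.1201 = 0.152, which adds 0.031. Ceiling 0.541.
- A single non-randomised test first reaches 80% at 44 patients (reject at ≥ 13; alpha 0.086, power 0.820).

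**What the listed boundaries can detect.** They reach an 80% chance of crossing only at a true DLT rate of 45.7% (mutant) or 47.1% (WT).

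**The case against.** The strongest reply is that the plan hides nothing. The true stopping probabilities and expected sample sizes are printed at the end of the section, and the boundaries are whole numbers that a monitor can apply without reading the power sentence. The verb in that sentence may also describe a design input, with the achieved values given separately. Other oversight exists: section 14.1 has a notification route ("For any increase in frequency of grade 3 or above adverse events" above the reported rate), and section 14.2 lets the DSMC suspend or close the study.

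This limits the harm but does not remove the contradiction. An 80% design input cannot be met with 16 or 20 patients at 10% type I error, and the text does not say so. Sections 14.1 and 14.2 set no numeric Phase II DLT boundary.

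Two further points stand as qualifications:

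- **Basis for the mutant figure.** At 20 patients no planned accrual is left to halt, so 37.0% is the figure that matters for conduct. On that basis the shortfall is 43 points (80 − 37.0). The 45.6% is the more generous reading.
- **Completing accrual.** The chance of no crossing describes the toxicity rule alone. The Simon first stage also stops cohorts, with probability 55.2% (mutant, at most 2 of 8) and 59.9% (WT, at most 1 of 9) at the null response rates. If DLT and response are independent, full accrual with no toxicity crossing at a 35% DLT rate is then about 24% (0.448 × 0.544) and 22% (0.401 × 0.543). At the alternative response rates it is about 50% in each cohort.

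**Conclusion.** The stated 80% power is wrong. Taken alone and with all listed looks counted, the toxicity rule is never crossed at a 35% DLT rate with probability 54.4% (mutant) and 54.3% (WT), where 80% power would mean 20%.

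The boundary table, the inequality, the worked example and the printed operating characteristics all agree with one another; the power sentence is the outlier. The 10% type I error holds only as an upper limit, since the achieved values are 5.8% and 7.3%.

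The calculation assumes independent patients with a common DLT rate and complete DLT status at each look. The point should be fixed, but its consequence is limited: no sample size, boundary or efficacy analysis depends on the 80%.

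**What to change.** In section 13.2.1, delete the 80% power statement, describe 10% as an upper limit on type I error, and give the achieved figures on a stated basis. For example:

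> The boundaries keep the probability of crossing at a DLT rate of 20% below 10%. At DLT rates of 20% and 35%, the probability of stopping before full accrual is 4.8% and 37.0% in the FLT3-mutant cohort (5.8% and 45.6% if the look at 20 patients is counted) and 7.3% and 45.7% in the FLT3-WT cohort.

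This needs no extra patients and no change to the boundaries or to conduct. The cost is that the stated sensitivity becomes less favourable. Whether that sensitivity is enough is for the sponsor to decide; with type I error held at 10%, no redesign within 20 and 16 patients could take it above 60.4% and 54.1%.

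### The last FLT3-WT toxicity look (more than 6 of 16) cannot be crossed by a cohort that passed the look at 15 patients, so it adds nothing to detection

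*Combined protocol and SAP*

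**What the plan says.** Section 13.2.1 sets up sequential toxicity monitoring for each phase II cohort: "we will look at the toxicity data in real time for every 3 patients, separately among the two phase II cohorts". The design rates are explicit: "A DLT rate of 20% would be considered as acceptable while a DLT rate of 35% would be considered as too high and unacceptable". So are the error rates: "The type I error is chosen to be 10% and the power is chosen to be 80" per cent. Accrual is halted "if the number of dose-limiting toxicities is $>$ the following boundary b out of n patients currently studied", and the worked example confirms the strict inequality: "if among the first 6 patients, there are more than 3 DLTs, then the accrual for the corresponding cohort would be paused".

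The two lists are:

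- WT, maximum 16 patients: "for the Flt3WT cohort, the boundary will be $b/n=2/3$, 3/6, 4/9, 5/12, 5/15, 6/16".
- Mutant, maximum 20 patients: "for the Flt3mut cohort, the boundary will be $b/n=2/3$, 3/6, 4/9, 5/12, 6/15, 7/18, 7/20".

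The section describes the method this way: "This is a Pocock-type boundary where the same significance level is used for all looks". For WT it reports early stopping of about 7.3% (expected sample size 15.6) at a true rate of 20%, and about 45.7% (13.6) at 35%. For the mutant cohort the figures are 4.8% (19.5) and 37% (16.3).

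**The concern.** The WT list has a look at 15 and another one patient later, and the boundary rises by one between them. Under a strict rule that step leaves the last look nothing to detect. The section therefore presents six WT decision points when only five can act, and the verdict on the fully enrolled WT cohort is fixed at patient 15. The rule already detects an unacceptable DLT rate less than half the time, and part of the 10% type I error that the plan allows itself is not spent. A committee that applies the table could take the sixth look for a real check.

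**Working it through.** **Inputs (all from section 13.2.1).** Boundaries as listed; cross only if the DLT count X exceeds b; true rates p = 0.20 and 0.35. The WT maximum of 16 (9 + 7) is in section 13.2.

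**Method.** Let f_j(x) be the probability of x DLTs at look j with no boundary crossed earlier. With m new patients since the previous look:

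- f_j(x) = Σ over y ≤ b_(j−1) of f_(j−1)(y) · C(m, x−y) · p^(x−y) · (1−p)^(m−x+y)
- crossing probability at look j: c_j = Σ over x > b_j of f_j(x)
- expected N = Σ c_j·n_j + (1 − Σ c_j)·n_max

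**Step 1: reproduce the plan's WT figures.**

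| Look | 3 | 6 | 9 | 12 | 15 | 16 | Total |
|---|---|---|---|---|---|---|---|
| b | 2 | 3 | 4 | 5 | 5 | 6 | |
| p = 0.20 | .0080 | .0131 | .0101 | .0073 | .0351 | 0 | .0735 |
| p = 0.35 | .0429 | .0863 | .0771 | .0645 | .1859 | 0 | .4567 |

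Expected N is 15.63 and 13.60. These match the stated 7.3%, 45.7%, 15.6 and 13.6. Reading the rule as at or above b gives 24.4% and 70.6%, which do not match, so the strict reading is the intended one.

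**Step 2: the last look.** Passing n = 15 means X ≤ 5. After one more patient X ≤ 5 + 1 = 6, and crossing needs X ≥ 7. Hence c_16 = 0 for every p.

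**Step 3: the mutant list for comparison.** Crossing before the n = 20 look is .0475 and .3702, matching the stated 4.8% and 37%. The n = 20 look adds .0108 and .0858, for totals of .0583 and .4560. Two things follow. A reachable final look is worth 8.6 points at 35%. And the plan's early-stopping figures leave out the final look.

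**Step 4: more than 5 of 16.** This adds the paths that stand at exactly 5 of 15 and then have a DLT in patient 16:

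- p = 0.20: .0946 × 0.20 = .0189; total .0735 + .0189 = .0924
- p = 0.35: .1947 × 0.35 = .0682; total .4567 + .0682 = .5249

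Expected N does not change, because enrolment is complete by then.

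**Step 5: is there a single nominal level?** For counts, a same-level boundary takes the smallest b with P(X > b | n, 0.20) ≤ a at every look.

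- WT as printed needs a ≥ 6.1% (5/15) and a < 7.3% (5/12), so a single level exists.
- Mutant as printed needs a ≥ 3.2% (7/20) and a < 5.1% (7/18), so a single level exists.
- 5/16 needs a ≥ P(X ≥ 6 | 16, 0.20) = 8.2%, which is incompatible with keeping 5/12.

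**Step 6: a same-level list that acts during accrual.** A level from 7.3% to just under 8.2% moves 5/12 to 4/12 and keeps 5/15. It would still print 6/16, which again cannot be crossed, so the n = 16 entry is dropped.

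| Look | 3 | 6 | 9 | 12 | 15 | Total |
|---|---|---|---|---|---|---|
| b | 2 | 3 | 4 | 4 | 5 | |
| p = 0.20 | .0080 | .0131 | .0101 | .0482 | .0151 | 9.4% |
| p = 0.35 | .0429 | .0863 | .0771 | .2213 | .0722 | 50.0% |

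**The case against.** The strongest reply is that nothing goes wrong in operation. The rule's only action is to halt accrual, and at 16 patients WT accrual is over, so a crossing there would stop nobody. Investigators also review safety continuously, and the monitoring committee may suspend or close the study (sections 14.1 and 14.2). This stands as a limit on weight: a reachable look at 16 would flag a completed cohort, not protect later WT patients. It does not excuse the entry. The plan lists a full-enrolment look in both cohorts under a stated 10%/80% test, and only the WT one cannot act.

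A second reply is that the zero is a by-product of one nominal level combined with a look one patient after 15. That is right, and nothing shows a typing error. It does not follow that the printed list is the tightest same-level choice within 10%; the list in Step 6 is tighter at 9.4%.

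A third reply is that the look is not strictly unreachable. DLTs are assessed over two cycles (section 5.4), and 13.2.1 requires no accrual hold while outcomes mature. A late DLT among the first 15, or accrual resumed after a pause, could produce 7 of 16. The conclusion is conditional on that point.

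A reader might infer more than the documents support:

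- **That the lists are not Pocock-type.** Their attained levels differ from look to look, but that is discreteness; each list fits one nominal level.
- **That 6 DLTs in 15 halting WT but not the mutant cohort is an inconsistency.** It follows from separate boundaries for different maximum sizes.
- **That ending at 6 of 16 (37.5%) contradicts the 35% limit.** The first is an observed rate and the second a true rate. Earlier boundaries tolerate higher observed rates (4/9, 5/12), and 6 of 16 without any crossing also occurs 1.9% of the time at a true 20%.

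**Conclusion.** The point holds in a limited form. With complete DLT counts at 15 and no resumption after a pause, the WT look at 16 contributes exactly zero crossing probability, against 8.6 points at a true 35% for the mutant cohort's last look. The published WT early-stopping probabilities and expected sample sizes are correct and should stand.

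A reachable last look would raise total WT detection at 35% from 45.7% to 52.5%, at a total false-alarm rate of 9.2%. The gain is modest. The larger gap is between the chosen 80% power and what any of these lists delivers: 45.7% for WT as printed, 45.6% for the mutant cohort including its last look, and 50.0% or 52.5% for the alternatives.

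**What to change.** Reconcile the WT entries at 15 and 16 in section 13.2.1 in one of these ways:

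1. **Delete the n = 16 look** and state that WT monitoring ends at 15. No operating characteristic changes.
2. **Use more than 5 of 16.** Total crossing becomes 9.2% and 52.5%. Describe it as a flag on the completed cohort and as a deliberate departure from a single nominal level. Early stopping stays at 7.3% and 45.7%, with expected N 15.6 and 13.6.
3. **Use 2/3, 3/6, 4/9, 4/12, 5/15.** This keeps a single level and acts during accrual, with 9.4% and 50.0%. Expected N, from the formula and the Step 6 table, becomes 15.5 at 20% and 13.1 at 35%; both stated WT sample sizes and probabilities would be replaced.

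With option 2, report total crossing separately from early stopping for both cohorts; the mutant totals are 5.8% and 45.6%. In every case replace the 80% power statement with the detection the chosen rule achieves, and state how DLTs still pending at a look are counted. The cost is one or two table entries and a few restated figures. The WT false-alarm rate rises from 7.3% to at most 9.4%, inside the 10% already allowed.

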13.3 Randomization and Stratification

For the Phase I study, patients will be enrolled in successive dose cohorts. In the phase II portion of the study, patients will be enrolled in 2 different cohorts based upon their Flt3 mutation status. No randomization is planned for this study.

13.4 Populations for Analysis

The populations used for analysis will include the following:

- **Safety population:** Patients who receive at least 1 dose of TAK-659 and Ixazomib will be used for all safety and analyses.
- **Pharmacokinetic population:** Patients who have at least one measurable post TAK-659 dose concentration.
- **Pharmacodynamics population:** Patients with sufficient dosing in Cycle 1 and sufficient pharmacodynamics data will be used for PD analyses.
- **Response-evaluable population:** Patients who receive at least 1 dose of study drugs, have measurable disease at baseline, and 1 postbaseline disease assessment will be used for analyses of response.
- **DLT-evaluable population:** the DLT-evaluable population is defined as all patients in the phase I portion of the study who either experience DLT during Cycle 1 or complete at least 75% of the planned doses of TAK-659 and Ixazomib within 2 cycles and have sufficient follow-up data to allow the investigators and sponsor to determine whether DLT occurred.

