5.1 Number of Patients

For the phase I portion, up to 18 patients will be enrolled in this study from approximately 2 to 4 study centers in the US. For the phase II portion, 36 patients will be enrolled from these centers.

Patients who are withdrawn from treatment during Cycle 1 for reasons other than toxicity during the phase I portion of the study will be replaced. Patients in the phase II portion of the study, beyond the Simon's two-stage threshold, who are not evaluable for response will be replaced; however, patients who receive at least 1 dose of study drugs, and have measurable disease on bone marrow exam or by biopsy-documented extramedullary tumor at baseline, will be used for futility analyses, including the Simon's two-stage response evaluation.

Duration of Study

Patients, including those who achieve a CR, may receive the combination until they experience disease progression. Patients will discontinue treatment if they have an unacceptable drug-related toxicity. The maximum duration of treatment, however, will be 12 months from Cycle 1 Day 1 (C1D1) unless it is determined that a patient would derive benefit from continued therapy beyond 12 months.

Patients will be followed for 30 days after the last dose of the combination, or to the start of subsequent anticancer therapy, whichever occurs first, to permit the detection of any delayed treatment-related AEs. All patients, including those patients no longer on treatment, will be assessed for survival. Patients who discontinue the study, regardless of reasons for discontinuation, will be followed for up to 12 months after discontinuation of the study drug for survival (every month until death), loss to follow-up, or withdrawal of consent for further follow-up. In addition, information on any subsequent anticancer therapies will be collected during the survival follow-up period. For patients who achieve CR but discontinue study treatment while still in remission, disease progression based upon available local data will also be collected during the survival follow-up period.

The final analyses for the clinical study report may be conducted after all patients enrolled in the study have had the opportunity to complete 3-4 cycles of combination therapy (while still not progressing).

It is anticipated that this study will last for approximately 24-32 months, including 9 to 12 months in the phase I portion, and 15 to 20 months in the phase II portion.

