5.3 Dose Escalation Rules and MTD Definition

Dose escalation will be determined based on the number of toxicities as noted by the algorithm noted in the following Figure 5-1.

Figure 5-1 Dose/Schedule Escalation Algorithm TAK-659 and

TAK-659/Ixazomib Clinical Study Protocol

If 2 or more patients in any dose level experience DLT, enrollment at that dose level will stop. Following consultation between the sponsor and investigators, either the previous dose level will be considered the MTD (if 6 or more patients have been studied at that dose level), the previous dose level will be expanded (if fewer than 6 patients have been studied at that dose level), or a dose level intermediate between the current and the previous dose level will be evaluated.

To define the Maximum Tolerated Dose (MTD), subjects will be evaluated for DLT following two cycles (56 days) of treatment. Decisions to move to next dose escalation cohort will not be made until all subjects complete 2 cycles of therapy at a given dose.

The MTD is defined as the dose level at which fewer than 33% of subjects experience a dose limiting toxicity (DLT), and specifically is the dose level at which less than 2 out of 6 subjects experience DLT. The minimal safe and effective dosing with pharmacodynamic and pharmacokinetic parameters pointing toward the goal of efficacy optimization, will be the recommended dose (RP2D) for the Phase II component of the study. To achieve this, the developing results of safety, tolerability, efficacy, PK and PD in each dose-escalation cohort will be reviewed in real time after each cohort, to determine whether maximal safety and evolving efficacy milestones will have been reached based on examination of two consecutive cohorts, when safety and tolerability measures are within criteria for each.

- The criterion for safety will be DLT <20% within the cohort.
- The criterion for tolerability will be the administration of >80% of expected dose within the cohort.
- The criterion for efficacy will be the dose with an estimation of greater or equal to 25% ORR in the Flt3 mutant cohort, or greater than or equal to 10% ORR in the Flt3 wild-type cohort.
- The criterion for optimizing PK will be: on day 1, equal or greater than 100ng/ml peak (Cmax) TAK-659, or its trough equal or greater than 15ng/ml; on day 15, peak at least 200ng/ml, trough at least 40ng/ml. On the other hand, the day 15 peak should be less than 400ng/ml, and trough should be less than or equal to 100ng/ml.

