- The criteria for defining an optimization of PD will be the reduction in more than one of the epigenetic drivers by 50%: JUN, ID1, β -catenin, HOXA 9/10, MEIS1 or rise by 50% of the epigenetic repressor RUNX3.

Subjects will initially be enrolled onto dose level 1. Three to six evaluable subjects will be enrolled at each dose level. All subjects assigned to a dose level must be followed for at least 2 cycles before dose escalation to the next cohort level can begin.

Note: Subjects not evaluable for DLT assessment (i.e. do not complete at least 1 cycle of therapy due to reasons other than toxicity) on the Phase I portion of the protocol will be replaced for determination of dose escalation.

The following rules will be followed:

- An initial three subjects will be enrolled in cohort 1. If all 3 subjects in cohort 1 complete 2 cycles of therapy without dose limiting toxicity (DLT), the study will proceed to enroll 3 subjects at cohort 2. If all 3 subjects in cohort 2 complete 2 cycles of therapy without DLT, the study will proceed to Phase II with the MTD of each drug established.
- Alternatively, if 1 of the first 3 subjects in any given dose cohort experiences DLT, an additional 3 subjects will be enrolled at that dose level. If only 1 of the total 6 subjects in a dose level experience DLT, the study will proceed to the next dose level as planned. If 2 of the total 6 subjects in any given dose cohort experience DLT, the next lower dose level will be explored and considered the maximum tolerated dose (MTD) if no more than 1 of 6 subjects experience a DLT. That dose will be recommended for the Phase II study.

Number of subjects with DLT at given dose level	Escalation decision
0 out of 3	Enter 3 subjects at the next dose level.
≥ 2 out of 3	Dose escalation will be stopped. This dose level will be declared the maximum administered dose . Three (3) additional subjects will be entered at the next lower dose level if only 3 subjects were treated previously at that next lower dose level.
1 out of 3	Enter at least 3 more subjects at this dose level: 
 • If 0 of these additional 3 subjects experience DLT, proceed to the next dose level. • If 1 or more of these additional 3 subjects experience DLT, then dose escalation is stopped and this dose is declared the maximum administered dose. Three (3) additional subjects will be entered at the next lower dose level if only 3 subjects were treated previously at that dose.

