5.4 Definition of Dose Limiting Toxicity

Toxicity will be evaluated according to the NCI CTCAE version 5.

DLT is defined as any of the following events occurring within the first 2 cycles that are considered by the treating physician to be at least possibly related to therapy with study drug(s). AEs in which the relationship to study drug cannot be ruled out should be considered possibly related to study drugs TAK-659 and/or Ixazomib.

- Prolonged myelosuppression with the persistence of \geq Grade 4 neutropenia or thrombocytopenia in the absence of leukemia (blast count <5% in bone marrow) at least 42 days after the initiation of therapy.
- Any Grade 3 or greater nonhematologic toxicity with the following exceptions:
 - Grade 3 nausea and/or emesis resolved to \leq Grade 1 or baseline in a week after the use of an optimal antiemetic regimen based on standard practice. The optimal antiemetic regimen is defined as an antiemetic regimen that employs both a 5-hydroxytryptamine 3 serotonin (5-HT3) antagonist and a corticosteroid given in standard doses and according to standard schedules. Grade 3 nausea, vomiting must not require tube feeding, total parenteral nutrition, or require prolonged hospitalization.
 - Grade 3 diarrhea that resolved to \leq Grade 1 or baseline in a week after receiving the maximal supportive therapy based on standard practice. Grade 3 diarrhea must not require tube feeding, total parenteral nutrition, or require prolonged hospitalization.
 - Brief (<1 week) Grade 3 fatigue.
 - Electrolyte abnormalities correctable within 72 hours

- Grade 3 or 4 tumor lysis syndrome if it is successfully managed clinically and resolves within 7 days without end-organ damage.
- Failure to administer $\geq 75\%$ of planned doses of the study drug due to TAK-659- or Ixazomib-related or possibly related hematologic (considered not related to leukemic infiltration) or nonhematologic toxicities.
- Other TAK-659- or Ixazomib-related Grade 2 or greater nonhematologic toxicities that, in the opinion of the investigator, require a dose reduction or discontinuation of therapy.
- Confirmed Hy's law/guideline cases of drug-induced liver injury: ALT or AST $>3\times$ upper limit of normal and total bilirubin $>2\times$ ULN, which is not cholestatic (ALT value \div ALT ULN) \div [Alkaline phosphatase value \div Alk phos ULN] $= <2$), and not caused by disease. This will require permanent drug discontinuation.

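### Three Phase I DLT rules are wrong as written: the 13.4 evaluable set leaves out some Cycle 2 DLTs, the 5.3 cohort-2 bullet declares an MTD after 0/3 at 3 mg, and 5.3 gives two 21-day cycles as 56 days

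*Combined protocol and SAP*

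**What the plan says.** **Evaluability.** Section 5.4 sets the window: "DLT is defined as any of the following events occurring within the first 2 cycles". Section 13.4 builds the DLT-evaluable population from Phase I patients "who either experience DLT during Cycle 1 or complete at least 75% of the planned doses of TAK-659 and Ixazomib within 2 cycles", who must also have enough follow-up for a DLT decision. Section 5.3 has its own evaluability note for escalation, which replaces "Subjects not evaluable for DLT assessment (i.e. do not complete at least 1 cycle of therapy due to reasons other than toxicity". Section 5.1 likewise provides that patients "withdrawn from treatment during Cycle 1 for reasons other than toxicity during the phase I portion of the study will be replaced".

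**Escalation after cohort 2.** Section 5.2 tabulates three cohorts, all at TAK-659 100 mg, with ixazomib at 2.3, 3 and 4 mg. It escalates ixazomib after cohort 2 if fewer than 2 of 6 patients have a DLT. The decision table in 5.3 sends 0 of 3 to the next dose level, and a bullet there sends 1 of 6 at any level onward as well. The bullet before it says that three DLT-free patients in cohort 2 take the study to Phase II with the MTD established. Section 5.3 defines the MTD by fewer than 2 DLTs in 6 subjects. Sections 5 and 13.2 require at least 6 patients at the MTD/RP2D.

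**Window length.** Section 5.3 states that "subjects will be evaluated for DLT following two cycles (56 days) of treatment". The cycle is 21 days in Section 5 and in both study calendars.

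**The concern.** The MTD/RP2D is the Phase I primary endpoint and sets the dose for up to 36 Phase II patients, so the rules that produce it should give one answer.

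On the first rule, the population that Section 13 names for DLT assessment can leave out a patient whose event is a DLT by definition. Among those left out are patients whom the plan itself takes off treatment, for example for Grade 3 or worse pneumonitis (5.2.2) or a confirmed Hy's law case (5.4).

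On the second rule, the same result in cohort 2 leads to two incompatible instructions: declare the MTD at 3 mg, or open 4 mg. Taken together the rules also run backwards, because 1/6 at 3 mg escalates while the cleaner 0/3 stops.

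The third is a plain error in the length of the DLT window.

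**Working it through.** **1. Doses against the 75% threshold in 13.4.** Inputs from Sections 5 and 5.6: TAK-659 daily on Days 1-15 and ixazomib on Days 1, 8 and 15 of each cycle.

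- Planned over two cycles: TAK-659 2 × 15 = 30; ixazomib 2 × 3 = 6.
- 75% of each: 0.75 × 30 = 22.5, so 23 doses; 0.75 × 6 = 4.5, so 5 doses.

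With full Cycle 1 dosing:

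| Last dose | TAK-659 | Ixazomib | Reaches 75% of both |
|---|---|---|---|
| C2D1 | 16/30 = 53% | 4/6 = 67% | No |
| C2D7 | 22/30 = 73% | 4/6 = 67% | No |
| C2D8 | 23/30 = 77% | 5/6 = 83% | Yes |

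A DLT that ends dosing on C2D1 to C2D7 therefore meets 5.4 but neither route into 13.4. If one ixazomib dose was missed in Cycle 1, all three Cycle 2 doses are needed (2 + 3 = 5), and the gap runs from C2D1 to C2D14. A patient who resumes and reaches 75% of both drugs stays in the set.

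Illustration of the reporting effect: leaving out one such patient turns 2/6 = 33% into 1/5 = 20%. Even then 5.3 is not met, since "The criterion for safety will be DLT <20% within the cohort" and 20% is not below 20%.

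**2. Cohort 2, rule by rule.**

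| Result at ixazomib 3 mg | 5.3 bullets | 5.3 table | 5.2 |
|---|---|---|---|
| 0/3 | Phase II, MTD established | Next dose level | Cohort 3 at 4 mg |
| 1/6 | Next dose level | Next dose level | Cohort 3 at 4 mg |

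Only the 0/3 cell of the bullets disagrees. It also names an MTD on 3 subjects where the definition uses 6.

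How often the conflict is triggered: P(0/3) = (1 − p)³. Taking p from the acceptable and unacceptable DLT rates in 13.2.1 (set there for Phase II, borrowed here as reference values):

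- p = 0.20: 0.80³ = 0.512, or 51%.
- p = 0.35: 0.65³ = 0.275, or 27%.

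These are chances of meeting the conflict, not of choosing a wrong dose.

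**3. Window.** 2 × 21 = 42 days. The stated 56 days is reproduced only by 2 × 28.

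**The case against.** **On 13.4.** No analysis section assigns a DLT rate to this population. Section 13.7.1 tabulates toxicity overall and by dose level, 13.10 uses the safety population, and 14.3 reviews every toxicity event for each subject before a dosing decision. An early Cycle 2 DLT appears in all three. This stands, and it confines the point to any DLT rate that does use the 13.4 set. The definition still contradicts 5.4.

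**On cohort 2.** The opening of 5.2 mentions only the step from 2.3 to 3 mg, 5.3 allows an RP2D review after two consecutive cohorts, and the DSMC must approve each dosing decision. But the same part of 5.2 tabulates 4 mg and names it as the maximum. The RP2D review weighs safety, tolerability, efficacy, PK and PD; it is not an automatic MTD after 0/3. DSMC approval does not say which rule to apply. Figure 5-1 could not be read in the text available, so I make no claim about what it shows.

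**On 56 days.** The operative gates are written in cycles ("Decisions to move to next dose escalation cohort will not be made until all subjects complete 2 cycles of therapy at a given dose"), and 56 exceeds 42, so observation cannot be cut short. That stands; the item is minor.

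**Further defects a reader might infer, which the documents do not support:**

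- *Section 6.1.1 limits the myelosuppression DLT to Cycle 1.* The drug hold described there keeps the patient in Cycle 1 up to day 42, so the wording is consistent.
- *The dosing-shortfall DLT in 5.4 (under 75% "of planned doses of the study drug due to TAK-659- or Ixazomib-related or possibly related hematologic" or nonhematologic toxicity) has no time frame.* It sits under the two-cycle lead-in, which supplies one.
- *A patient without a DLT who leaves early in Cycle 2 must be replaced.* A last dose on C2D1 to C2D7 is study day 22 to 28. Thirty days of safety follow-up reaches day 52 to 58, past day 42, although AE recording stops earlier if new anticancer therapy starts. Replacement may be chosen, but the plan is not shown to need it.

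**Conclusion.** Three Phase I rules need correcting.

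1. The DLT route into the 13.4 set is one cycle too short. How many patients this would affect is unknown, because the documents give no DLT timing.
2. The cohort-2 bullet contradicts the decision table in its own section, the 4 mg cohort in 5.2 and the six-patient requirement. This is the most consequential of the three, because its trigger is a common result: 27% to 51% at DLT rates of 35% and 20%, assuming independent patients with a common DLT rate.
3. The 56 days should be 42; this is a wording error.

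Two stronger conclusions are tempting. One is that escalation would undercount DLTs. It would not: 5.2 to 5.4 and 14.3 count a Cycle 2 DLT, and 5.1 and 5.3 replace only patients who leave for reasons other than toxicity. The other is that Phase II could open on 3 patients. The six-patient requirement in Section 5 bars that. What remains is an unsettled instruction about the dose, not a demonstrated wrong dose.

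**What to change.** - **13.4:** extend the DLT route from Cycle 1 to Cycles 1-2. Leave the 75% route as it is.
- **5.3, cohort-2 bullet:** 0/3 in cohort 2 opens cohort 3 (ixazomib 4 mg). Phase II opens only after at least 6 evaluable patients at the chosen dose with at most 1 DLT in 6. Check Figure 5-1 against this.
- **5.3, window:** replace 56 days with 42 days.

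The first and third changes are wording only. The second makes escalation slightly slower and may need up to 3 more patients at the chosen dose. Three cohorts of six make 3 × 6 = 18, which is the planned Phase I maximum.
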